14.2.1 Definitions

SRI-4 response among serologically active subjects

The SRI-4 response will be analyzed at Week 52 among subjects who are serologically active at screening, i.e., positive anti-dsDNA or low complement levels.

Time to first severe (BILAG A) flare

A severe (BILAG A) flare is defined as at least one BILAG A score in any organ system due to items that are new or worse, compared to the BILAG evaluation at the previous visit, during the 52-week treatment period. “Due to items that were new or worse” means that if the assigned Grade A/B or C contains ANY ITEM which is WORSE or NEW, such grade will be included into the flare consideration. This is valid for clinical organ domains. For laboratory organ domains (i.e. renal and hematological) where items are not worse/new, there has to be an increase in score from B to A or C to B for flare to be considered. Appendix 18.1.1 provides further details on BILAG evaluation. EAC will review the dry-run BILAG analysis dataset to ensure appropriateness and correctness of programmed BILAG flare derivation. Further details can be found in the EAC Charter.

Since subjects are only to be assessed for BILAG flare at discrete planned visits, the corresponding date of visit will be used to derive the time to first severe (BILAG A) flare as follows:

$$\begin{aligned} & \textit{Time to first severe BILAG A flare (days)} \\ &= \textit{Date of visit where the first severe BILAG A flare has been diagnosed} \\ & - \textit{Date of randomization} + 1 \end{aligned}$$

The following censoring rules will be used:

- A subject discontinuing the 52-week treatment period prior to Week 52 without severe flare will have his/her time to first severe flare right-censored at the last time point at which flare could be assessed (i.e. treatment discontinuation date).
- A subject completing the 52-week treatment period without severe flare will have his/her time to first severe flare right-censored at Week 52.

Additionally, a sensitivity analysis will be performed based on Multiple imputation approach of severe flare at each visit up to week 52:

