- Monotone missing data structure will be created as follows: intermediate (non-monotone) missing data will be multiply imputed using the Markov chain Monte Carlo (MCMC) method and assuming MAR and multivariate log normality. The SAS procedure PROC MI with the MCMC option will be used with seed number = 2005270018. The number of burn-in iterations will be set to 200, which is the default value. Nevertheless, if diagnosis plots show that the convergence has not yet occurred, this will be adjusted.
- Then the response (Severe BILAG A: Yes/No) will be imputed with treatment group, race, region, SLEDAI-2K total score (<10; >=10) and response at previous visit covariates.
- Imputation will be repeated 1000 times. Then depending of the visit of censored observation or of response, the time to first severe BILAG A flare will be computed as described for the non- sensitivity analysis. Estimate and associated standard error of Cox regression analysis applied on each imputed sample will be combined using MIANALYZE SAS procedure with the Rubin’s rules as described in Appendix 18.9.

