                    SLEDAI_2K_screening / RL TIES=DISCRETE;
  Hazardratio TreatmentGroup / DIFF=REF;
run;
```

In addition to the Cox regression model, the subgroup analysis can be implemented using the following code:

```
proc phreg data=<dataset>;
  class TreatmentGroup(ref='Placebo') SLEDAI_2K_screening;
  model AVAL*CNSR(1) = TreatmentGroup SLEDAI_2K_screening
                    TreatmentGroup*SLEDAI_2K_screening / TIES=DISCRETE;
  Hazardratio TreatmentGroup / DIFF=REF;
run;
```

For trend test for key secondary endpoint time to first severe (BILAG A) flare:

```
proc phreg data=<dataset>;
  class TreatmentGroup Region Race SLEDAI_2K_screening / param=GLM;
  model AVAL*CNSR(1) = TreatmentGroup Region Race
                    SLEDAI_2K_screening / TIES=DISCRETE;
  ESTIMATE "Trend linear in treatment" TreatmentGroup -3 -1 1 3;
  CONTRAST "Trend linear in treatment" TreatmentGroup -3 -1 1 3 / e;
run;
```

Sensitivity analysis of first severe BILAG A flare:

```
/******
  STEP 1 : creation of monotone missing data structure
******/

/** _burn-in_NBITER_ will have to be adjusted by a convergence plot,
if convergence is not yet diagnosed after 200 iterations ***/
title "Step 1 : Create monotone structure" ;
proc MI data=<Dataset> out=outMAR1 seed=&seed. nimpute=&nimpute. noprint;
  var
  TreatmentGroup
  black (0=non-black 1=black)
  SLEDAI_2K_screening
  US (0=not US 1=US region)
```

```
West (0=not Western Europe, 1=Western Europe region)
Jap (0=not Japan region, (1=Japan region)

Resp_base Resp_Day14-Resp_Day52;

/* continue to the last endpoint */

;
mcmc chain=single initial=EM nbITER=200 NITER=100 impute=monotone ;
EM MAXITER = 5000 ;
run ;

/*****
STEP 2 : Apply multiple imputation
*****/
title "Step 2 : Apply MI procedure (MAR pattern)" ;
proc mi data=outMAR1 nimpute=1 seed=&seed. out=outMAR2 noprint;
  by _Imputation_;
  class TreatmentGroup race region SLEDAI_2K_screening
    Resp_base Resp_Day14-Resp_Day52;
  var TreatmentGroup race region SLEDAI_2K_screening
    Resp_base Resp_Day14-Resp_Day52;
  monotone logistic;
run;

/*****
STEP 3 : Create dataset with Time to
*****/
This should be define in specification of ADAM and same rule should be applied to
outMAR2 dataset by imputation.

/*****
STEP 4 : Create estimate on imputed dataset
*****/
proc phreg data=<dataset>;
  by _Imputation_;
  class TreatmentGroup(ref='Placebo') Region Race SLEDAI_2K_screening;
  model AVAL*CNSR(1) = TreatmentGroup Region Race

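### The flare multiple-imputation analysis imputes visits to Week 52 but, as written, still censors flare-free discontinuers at discontinuation, so it inflates flare risk and shifts the hazard ratio when drop-out is unequal

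*SAP*

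**What the plan says.** SAP 14.2.1 announces a "Multiple imputation approach of severe flare at each visit up to week 52". The yes/no flare indicator is imputed from treatment, race, region, SLEDAI-2K stratum and the response at the previous visit, 1000 times. Cox estimates are pooled by Rubin's rules.

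For the time variable in each imputed data set, the section says that "the time to first severe BILAG A flare will be computed as described for the non- sensitivity analysis". Step 3 of the sample code in 18.9.2 agrees: "This should be define in specification of ADAM and same rule should be applied to" the imputed data set.

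The rule referred to stands earlier in 14.2.1 and has two branches:
- Completers with no severe flare are censored at Week 52.
- A subject who discontinues before Week 52 without a severe flare is "right-censored at the last time point at which flare could be assessed (i.e. treatment discontinuation date").

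Section 14.2.2.2 and Table 18 list the stratified log-rank test, the Cox model, the Kaplan-Meier estimates and the Kaplan-Meier curves as outputs of this analysis.

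**The concern.** Imputation fills in flare status. It does not turn a discontinuer into a completer, so the discontinuation branch still applies to a discontinuer whose imputed visits are all flare-free. Take two subjects who stop at Week 12. One has an imputed flare at Week 40: this subject stays at risk to Week 40 and has an event. The other is imputed flare-free to Week 52: this subject leaves the risk set at Week 12. How long a discontinuer is followed thus depends on the imputed outcome. A correct imputation model, data missing at random and 1000 imputations do not remove this, because the derivation itself creates it.

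Table 18 lists two sensitivity analyses for this key secondary endpoint, a per-protocol repeat and this one. Only this one addresses missing data. If the derivation adds its own bias, neither agreement nor disagreement with the primary flare result can be read at face value.

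**Working it through.** The SAP gives no flare rate, hazard ratio or event count for this endpoint, so there is no figure to reproduce.

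**Inputs from the SAP.** 13 four-weekly analysis visits, Week 4 to Week 52 (Table 51); 1:1:1:1 allocation (8.2.1); 469 randomised for the primary analysis (8.2.2), so 469/4, about 117 per arm; discrete-logistic ties (14.2.2.2).

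**Assumptions.** Week 52 flare risk p of 15% (range 10% to 35%); drop-out D of 5% to 35% per arm; constant per-visit hazards; non-informative drop-out; correct imputation within arm. Section 8.2.1 plans for 5% drop-out for reasons other than efficacy or safety. Section 7 says that drop-out may be higher than expected, without a figure.

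**Formulas.** Let h = 1 − (1 − p)^(1/13) and d = 1 − (1 − D)^(1/13). Let q_k = (1 − d)^k be the share still on treatment at visit k, and S_k = (1 − h)^(k−1) the share truly flare-free before visit k.
- Events at visit k, observed plus imputed: S_k × h.
- Risk set under the written rule: S_k × [q_k + (1 − q_k) × (1 − (1 − h)^(14−k))]. The second term holds the discontinuers with an imputed flare still to come. Those imputed flare-free are missing.
- Estimated hazard at visit k: h / [q_k + (1 − q_k) × (1 − (1 − h)^(14−k))], which is above h whenever q_k < 1.
- With Week 52 censoring of the imputed data the risk set is S_k, the hazard is h and the risk is p.

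**Kaplan-Meier risk, p = 15%, D = 25%.** h = 0.01242.
- Visit 1: q = 0.9781; 0.01242 / (0.9781 + 0.0219 × 0.15) = 0.01266.
- Visit 13: q = 0.75; 0.01242 / (0.75 + 0.25 × 0.01242) = 0.01650.
- One minus the product of (1 − hazard) over the 13 visits is 17.2%, against a true 15.0%. With D = 5% it is 15.4%.

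**Hazard ratio, no true effect, p = 15%, drop-out 35% active and 15% placebo.** The ratio of hazards at a visit is the placebo bracket divided by the active bracket.
- Visit 1: 0.9894 / 0.9723 = 1.02.
- Visit 13: (0.85 + 0.15 × 0.01242) / (0.65 + 0.35 × 0.01242) = 0.8519 / 0.6543 = 1.30.
- Pooled over visits by the partial-likelihood score: 1.14.

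| Drop-out active / placebo | HR, true 1.00 (p = 15%) | HR, true 1.00 (p from 10% to 35%) |
|---|---|---|
| 25% / 25% | 1.00 | 1.00 |
| 30% / 20% | 1.07 | 1.06 to 1.07 |
| 35% / 15% | 1.14 | 1.12 to 1.15 |
| 15% / 35% | 0.88 | 0.87 to 0.89 |

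With a true benefit (20% placebo, 12% active, HR 0.571), the written rule gives 0.654 at 35%/15%, 0.502 at 15%/35% and 0.573 at 25%/25%. Week 52 censoring returns the true value in every scenario.

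**Timing of drop-out.** If drop-out falls just after a visit, so that q_k = (1 − d)^(k−1), the p = 15% results shrink slightly: 16.9% at D = 25%, and HR 1.06 and 1.12 at 30%/20% and 35%/15%.

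**Trial-size check.** 300 simulated trials per scenario, 117 per arm, 20% risk in both arms, 10 imputations, Rubin pooling. At 35%/15% the written rule gave 1.16, the unimputed analysis 1.02 and Week 52 censoring 1.02. At 15%/35% the values were 0.87, 0.98 and 0.98. At 25%/25% there was no shift.

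**The case against.** **The text may have meant something else.** The sentence that refers back to the primary rule opens by making the time depend on the visit of censoring or of response. In a completed data set the last visit with a flare value is Week 52, which could also be the last time point at which flare could be assessed. In Table 18 the MI row is the only time-to-flare row that does not point to 14.2.1 for censoring, and Step 3 of the code defers to an ADaM specification that is not shown. This stands as evidence of possible intent. It does not supply a rule: no sentence says that imputed flare-free subjects are censored at Week 52, and the parenthesis in 14.2.1 names the treatment discontinuation date.

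**The effect is small beside sampling error.** With 117 per arm and 15% risk there are about 18 events per arm, so SE(log HR) is about √(1/18 + 1/18) = 0.33. A shift to 1.07 is about 0.2 SE and to 1.14 about 0.4 SE. This is true, but the shift is systematic and avoidable.

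**It is one sensitivity analysis.** This also stands. The analysis carries no alpha in 14.1.2.4, and results of the primary analysis had been reviewed before this SAP version (6.3, 6.4).

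Three stronger readings are tempting, and the documents support none of them:
- That the hazard ratio is biased in any case. It is not when drop-out is equal, and the SAP gives no drop-out by arm.
- That after discontinuation the risk set holds only future events. That is so only among discontinuers; subjects still on treatment remain in it.
- That the confirmatory flare result is compromised. It rests on unimputed data.

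**Conclusion.** The point holds for the plan as written. Imputing to Week 52 and then applying the primary censoring rule keeps imputed flares and drops imputed flare-free time among discontinuers. Kaplan-Meier flare risk is too high in every arm with drop-out: slightly at the 5% design figure, by about 2 percentage points at 25% with a true risk of 15%. The hazard ratio is distorted only if drop-out differs between arms, by about 6% to 15% when the gap is 10 to 20 percentage points, and always against the arm with more drop-out. If placebo loses more subjects, the error looks like a benefit. These sizes rest on assumed flare risks, assumed drop-out by arm and constant hazards; the direction follows from the derivation. The analysis should be corrected because it is the only missing-data check on this endpoint. The primary and hierarchical tests stay as they are.

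**What to change.** Add to 14.2.1, and repeat in Step 3 of the 18.9.2 code: in each imputed data set, an imputed severe flare is dated at the target day of its analysis visit (Table 51), and every subject with no observed or imputed severe flare is censored at Week 52 (Day 365), whether or not treatment was discontinued. The dating clause is needed because the time formula uses a visit date and an imputed visit has none. Table 51 counts days from first dose and the formula counts from randomisation, so the derivation should convert between them. In Table 18, point the MI row to this sentence.

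The cost is one sentence and one derivation line. Because the primary analysis has been reviewed, first check which rule the ADaM derivation used. If it used the discontinuation date, rerun this one analysis and report the change in the study report as a correction.

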14.2.2 Primary Analysis of Key Secondary Endpoints

The key secondary endpoints will be analyzed on mITT Analysis Set at Week 52, as indicated in

Table 18.

Table 18 : Analysis of the key secondary endpoints

Endpoint	Analysis	Analysis Population	Analysis Method	Data Handling Notes
SRI-4 response in serologically active subgroup	Primary Analysis	mITT Analysis Set	
 Presentation of Odds-Ratio (OR), 2-sided 95% CI of OR, nominal 1-sided p-value ($\alpha=0.025$) from Logistic Regression Number and percentage of responders in each dose group, observed Δ in response proportions from Placebo for each dose group 	A subject with a missing response at Week 52 will be considered a non-responder at Week 52.
	Sensitivity Analysis 1	PP Analysis Set	
 Presentation of Odds-Ratio (OR), 2-sided 95% CI of OR, nominal p-value from Logistic Regression Number and percentage of responders in each dose group, observed Δ in response proportions from Placebo for each dose group 	As the Primary Analysis
	Supportive analysis 1	mITT Analysis Set	
 Test of linear trend in log odds of response with increasing dose, based on an appropriate contrast from the logistic model, i.e., (3, 1, -1, -3). 	As the Primary Analysis
Time to first severe (BILAG A) flare	Primary Analysis	mITT Analysis Set	
 Stratified Log Rank Test for 1-sided p-values ($\alpha=0.025$) for comparison between treatment groups vs Placebo Cox Proportional Hazard model for Hazard Ratio (HR) and 95% CI of HR between each treatment group vs Placebo Presentation of product-limit estimates KM curves 	See Section 14.2.1 for censoring rules.
	Sensitivity Analysis 1	PP Analysis Set	
 Stratified Log Rank Test for p-values for comparison between treatment groups vs Placebo Cox Proportional Hazard model for HR and 95% CI of HR between each treatment group vs Placebo Presentation of product-limit 	See Section 14.2.1 for censoring rules.

			estimates	
			
 • KM curves 	
	Sensitivity Analysis 2	mITT Analysis Set	
 • Stratified Log Rank Test for p-values for comparison between treatment groups vs Placebo • Cox Proportional Hazard model for HR and 95% CI of HR between each treatment group vs Placebo • Presentation of product-limit estimates • KM curves 	For subjects with missing response at Week 52, the multiple imputation (MI) will be used to impute the missing data using the available observations.
	Supportive Analysis 1	mITT Analysis Set	
 • Test of dose response trend using the same Cox model as above 	See Section 14.2.1 for censoring rules.

14.2.2.1 SRI-4 response among serologically active subjects

For this analysis, a subject will be considered as a SRI-4 Non-Responder if the subject takes any EAC-determined protocol-prohibited medications during the treatment period. It will be confirmed by the EAC. In addition, a subject with a missing response at Week 52 will be considered a non-responder at Week 52.

The SRI-4 response at Week 52 among serologically active subjects will be based on the mITT Analysis set, and analyzed using logistic regression model for the odds of a given SRI response adjusted for the stratification variables used in the randomization (race: black vs non-black, screening SLEDAI-2K total score: <10 vs ≥10 and region: US and Western Europe vs Japan vs ROW) and with treatment as a factor. The estimated OR, together with associated two-sided 95% CI of the estimated OR and nominal one-sided p-value ($\alpha=0.025$) from the logistic regression model, comparing each evobrutinib treatment group to placebo will be presented. The multiplicity adjustment procedure as outlined in Section 14.1.2.4 will be applied to assess statistical significance.

The logistic model will be repeated on PP analysis set if the size of these analysis sets differs substantially (>10%) from mITT.

In addition, the number and percentage of SRI-4 responders and non-responders at Week 52 in each treatment group will be presented the same way as for the primary analysis (see Section 14.1.2.4).

SRI-4 response rates over time will be also presented by visit, using similar imputation rules as applied for the Week 52 timepoint.

14.2.2.2 Analysis of Time to first severe BILAG A flare

The time to first severe flare will be analyzed on the mITT Analysis Set using a stratified log rank test with treatment as main effect and stratification variables used in the randomization (race, screening SLEDAI-2K total score and region) as covariates. The one-sided p-values ($\alpha=0.025$) from the stratified log rank test for treatment comparisons vs placebo will be reported. The multiplicity adjustment procedure as outlined in Section 14.1.2.4 will be applied to assess statistical significance.

In addition, a Cox proportional hazards regression model including treatment as factor and the stratification factor at randomization as covariates will be performed. Ties will be handled by replacing the proportional hazards model by the discrete logistic model. The HR together with its 95% CI will be presented as determined by the proportional hazards model. Placebo group will be used as reference group. The assumptions of proportional hazards will be verified graphically (the curves representing the relative risk will be plotted for each treatment group and should be parallel).

KM estimates (product-limit estimates) will be presented by treatment arm together with a summary of associated statistics (median, Q1 and Q3, minimum and maximum) including the corresponding two-sided 95% CI of the median. The KM 5%, 10%, 15% and 20% percentiles as well as the corresponding 95% CI will also be presented. In addition, the number of severe flares by treatment group will be presented.

The KM curves will also be provided for each treatment group.

As sensitivity analyses, stratified log-rank test, Cox model, KM estimates and KM curves will be repeated:

- Using MI as stated in Section 14.2.1,
- On PP analysis set if the size of these analysis sets differs substantially (>10%) from mITT.

In addition, a test for trend in dose-response, using the same Cox model, will be reported as a supportive analysis, using contrast statement and (-3 -1 1 3) coefficients.

An example of SAS code is available in Appendix 18.9.

If there is model convergence problem due to for example zero cells in covariates, appropriate method will be applied to resolve the issue.

14.2.2.3 Subgroup Analysis

Time to first severe (BILAG A) flare

To assess numerically the consistency among the subgroups (Table 4) of time to first severe flare, the analysis will be performed on the mITT Analysis Set using the Cox proportional regression model with treatment, subgroup of interest, treatment by subgroup of interest

interaction as main effects. The estimated HR for treatment comparison with placebo, together with associated two-sided 95% CI of the estimated HR, nominal p-value from the model contrast will be presented for each treatment group. The same censoring approach will be used as the main analysis. No multiple testing adjustments will be performed.

A forest plot of the HR and the 95% CI of the hazard ratio between each treatment group and placebo will be presented for each category of the subgroups.

SRI-4 response among serologically active subjects

Primary analysis of SRI-4 response among serologically active subjects will be repeated for subgroup A from [Table 4](#) (HDA vs non-HDA). The estimated OR, together with associated two-sided 95% CI of the estimated OR, nominal p-values from the logistic regression model, comparing each evobrutinib treatment group to placebo will be presented. No multiple testing adjustments will be performed.

14.3 Other secondary endpoints

All other secondary endpoints will be analyzed for the PA using the mITT Analysis Set.

All statistical tests of the other secondary efficacy endpoints will be conducted at a two-sided α level of 0.05, with p-values considered nominal. P-values and the 95% CIs will be presented where applicable.

14.3.1 Disease Activity Endpoints

The following secondary endpoints to be analyzed on mITT analysis set are summarized in [Table 19](#). LLDAS is defined in [Appendix 18.1.7](#).

For SRI-4 and SRI-6 response endpoints as well as LDA status and LLDAS, the primary analysis method applied to the two-primary endpoints ([Section 14.1.2.1](#)) will be performed.

In addition, for LDA and LLDAS endpoints in [Table 19](#), the number and percentage of subjects with response or non-response will be summarized over time (by visit), using similar imputation rules as applied for the Week 52 timepoint.

Table 19 : Disease Activity Endpoints

Endpoint	Analysis method	Data Handling Notes

 • SRI-6 response at Week 52, in the serologically active subgroup • SRI-4 Response at Week 52 with a Sustained Reduction of OCS Dose to 7.5 milligrams prednisone-equivalent per day or less (≤ 7.5 mg/day) and less than or equal to (\leq) Day 1 dose during Week 41 Through Week 52, in all subjects • SRI-6 Response at Week 52 with a Sustained Reduction of OCS Dose to 7.5 milligrams prednisone equivalent per day or less (≤ 7.5 mg/day) and less than or equal to (\leq) Day 1 dose during Week 41 Through Week 52, in the HDA subgroup • SRI-4 Response at Week 52 with a Sustained Reduction of OCS Dose to 7.5 milligrams prednisone equivalent per day or less (≤ 7.5 mg/day) and less than or equal to (\leq) Day 1 dose during Week 41 Through Week 52, in the serologically active subgroup 	Same as the Primary Method in Table 17	Same as the Primary Method in Table 17

 • LDA status, defined by SLEDAI-2K ≤ 2 at Week 52 • LDA, defined by clinical SLEDAI-2K (SLEDAI-2K excluding anti-dsDNA and low complement parameters) ≤ 2 at Week 52 • LLDAS at Week 52 	Same as the Primary Method in Table 17	Same as the Primary Method in Table 17

In order to determine whether the subject had a sustained reduction of OCS Dose to ≤ 7.5 mg/day and \leq Day 1 dose during Week 41 Through Week 52, the daily dose of CS will be calculated for each analysis visit from Week 41 to Week 52, according to Appendix 18.8. If the condition is met for all days during this period, the subject will be considered as having a sustained reduction of OCS Dose.

